6.4.2.1 Prior to each cycle of adjuvant therapy

- Physical examination including vital signs
- WHO-ECOG performance status
- Toxicity according to CTCAE v.3
- Complete blood count, all serum chemistries

6.4.2.2 Day 21 (+/- 48 hours) of each cycle of adjuvant therapy

This is only needed in cycle 1 and in cycle 2 if the daily dosage is increased to 200 mg/m², or in case significant hematological toxicity was observed in the prior cycle:

- Complete blood count

6.5 After the documentation of first progression

The patient must be followed every six months, in particular for performance status, quality of life, cognition and for documentation of further treatments.

- Physical examination including neurological evaluation
- Corticosteroid intake
- MMSE
- Quality of Life C30 and BCM20
- WHO-ECOG performance status
- Documentation of further treatments

All patients will be followed until death.

6.6 Summary table

	Baseline		During radiotherapy w/wo Concomitant treatment		4 weeks after RTX	Follow up With or without adjuvant temozolomide		After first progression Every 6 months
	At registra- tion	Within 14 -28 days prior to random.	Weekly	Wks 4 and 6		Adjuvant treatment (bef. each cy) [Ⓜ]	Disease /Adverse Events assessment every 6 months	
Medical history		♦						
Phys. Exam. Vital signs		♦	♦	♦	♦	♦	♦	♦
Neurological Exam		♦		♦	♦		♦	♦
WHO-ECOG PS		♦		♦	♦	♦	♦	♦
QOL questionnaire		♦			♦		♦	♦
MMSE		♦			♦		♦	♦
Haematology		♦	Ⓜ	Ⓜ	♦	♦ [♫]		
Serum chemistry#		♦		Ⓜ	♦	♦		
Toxicity		♦	♦	♦	♦	♦	♦	
Brain Imaging		♦(£)			♦		♦	
Corticoid intake		♦		♦	♦		♦	♦
Paraffin blocks	♦							
Frozen material		∞						
Blood samples for LOH 1p/19q	♦							
Cognitive exam		∞*						

serum chemistry: electrolytes, transaminases, gamma-GT, alkal.phosph., creatinine, LDH, glucose

♦ mandatory Ⓜ mandatory only for temozolomide treated patients

♫ to be repeated at day 21 of the first cycle of adjuvant temozolomide; and in case the dosage in the second cycle is increased; and in case of significant hematological toxicity during the previous cycle

∞ optional translational research, dedicated centers only; * at baseline and at yearly intervals

(£) The initial assessment of disease with MR or CT must be performed between the surgery and the start of radiotherapy, unless patients underwent a biopsy only in which case the pre-operative imaging is sufficient (and only a CT for radiotherapy planning is required).

7 Criteria of evaluation

7.1 Progression free survival

Disease progression is defined as radiological or neurological/clinical progression (whichever occurs first); progression free survival (PFS) is the time interval between the date of randomization and the date of disease progression or death whichever occurs first. If neither event has been observed, the patient is censored at the date of the last follow up examination.

PFS will be assessed following the target lesion(s) as defined hereunder.

7.1.1 Schedule of disease evaluation

The initial assessment of disease (including MRI or CT) must be performed between the surgery and the start of radiotherapy, unless patients underwent a biopsy only in which case the pre-operative imaging is sufficient.

Follow-up assessments (including MRI or CT) will be performed as described in chapter 6 here above until disease progression (even after treatment discontinuation), or until the start of another treatment.

The use of MRI is strongly recommended.

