5.4 Withdrawal criteria

Whatever the disease status, treatment will be discontinued in case of

- Patient refusal
- Unacceptable toxicity precluding further therapy
- Best interest of the patient

Patients discontinuing therapy in the absence of progression should usually not receive other cancer treatment before their disease progresses, unless this is clearly not in the interest of the patient.

After progression, further treatment will be at the discretion of the treating physician. Any anti-cancer therapy other than the study regimen described in this protocol will not be considered as part of the protocol treatment.

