8.2.1.2 Progression-free Survival (secondary endpoint)

The Progression-free Survival (PFS) is calculated from the date of randomization up to the date of first progression or death (any cause) whichever comes first. In case a patient is still alive and without progression at the last follow up visit date, PFS will be censored at the date of last follow up visit date.

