8.2.1.3 Neurological deterioration-free survival (secondary endpoint)

The neurological deterioration-free survival (NPFS) is calculated from the date of randomization up to the date of first neurological deterioration (see section 7.2) or death (any cause) whichever comes first. In case a patient is still alive and without neurological deterioration at the last date of assessment of the WHO performance status, NPFS will be censored at that date.

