8.2.3.3 Analyses methods for safety endpoints

The safety analyses will be presented overall and by period as defined below:

- The baseline (BL) period will include all information recorded up to the randomization date.
- The radiation therapy (RT) or chemo/radiation period (RT&TMZ) will start on the day the radiation therapy is first given and end the day of the last administration of radiation therapy treatment plus 28 days.
- The adjuvant chemotherapy period (RT+TMZ) will start 29 days after the last dose of radiation therapy treatment and end-up 27 days after the first day of administration of the last cycle of adjuvant chemotherapy.
- The follow-up period (FUP) will start 29 days after the last dose of radiation therapy treatment or 28 days after the first day of administration of the last cycle of adjuvant chemotherapy.

The safety assessments include hematological toxicity, laboratory measurements and adverse events. Only the safety assessments performed before progression or within 7 days of progression and before start of any further anti-cancer therapy will be included in the analysis.

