8.3.2 New plan

Further to the original interim analysis, the IDMC formulated the following recommendations:

- To release and publish the results on all endpoints for the adjuvant TMZ comparison without delay.
- In doing, so, to pay particular attention to the impact on patients in arms 1-2, who may benefit from initiating adjuvant TMZ and for whom a therapeutic decision to initiate such treatment may ensue. In particular, those patients who are still receiving RTX (with or without concomitant TMZ), as well as those patients who have finished RTX treatment within the past three months.
- To continue the follow-up for the concurrent TMZ question. Because of the very long follow-up time required to reach data maturity for overall survival for this question, consideration may be given to implementing a further interim analysis. The IDMC would welcome proposals for a revised plan incorporating a second such interim analysis.
- To take the necessary steps to obtain data on the MGMT promoter status for all patients, including reanalysis of samples using more modern assays that may require less material than the early assays. The investigators should assess heterogeneity of results across subgroups.

A new interim analysis plan was designed by an independent statistician. It includes an additional interim analysis for both efficacy and futility analysis at 2/3 of information (356 deaths) using the original spending function (stopping boundary from Rho family ($Rho=2$)) for the efficacy and an O'Brien Fleming stopping boundary for futility. This analysis will be binding in order to keep the same number of events and the 80% power at the final analysis. Based on these new assumptions, the trial will be stopped for futility if $HR \geq 0.882$ and for early efficacy if $HR < 0.778$. $HR=0.882$ corresponds to OS rate at 2 years of 71.9% in the no concurrent TMZ chemotherapy arm versus 74.7% in the concurrent TMZ chemotherapy arm (less than 3% difference observed). The timing of this second interim analysis is at about 35 months after end of accrual i.e. September 2018. The final analysis is expected in 2022 at will be performed at a significance level of 0.044 ($HR < 0.841$).

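### Section 7.1.1 lets disease assessment stop when another treatment starts, yet PFS runs on to death or the last visit, so some progression-free time may rest on no scheduled imaging

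*Combined protocol and SAP*

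**What the plan says.** **Assessment schedule.** Section 7.1.1 has follow-up assessments, including MRI or CT, continue "until disease progression (even after treatment discontinuation), or until the start of another treatment". Section 6.4.1 and the table in 6.6 put all patients on six-monthly assessment with brain imaging after radiotherapy and do not mention a stop at new treatment. Section 6.5 gives a schedule without imaging, but only for patients who have already progressed.

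**PFS definition.** In section 7.1, "progression free survival (PFS) is the time interval between the date of randomization and the date of disease progression or death whichever occurs first". Without an event, "If neither event has been observed, the patient is censored at the date of the last follow up examination". Section 8.2.1.2 says that "PFS will be censored at the date of last follow up visit date". Neither section says what happens when another treatment starts first.

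**Other endpoints.** For neurological deterioration-free survival (NPFS), section 8.2.1.3 ties censoring to the assessment that defines the endpoint: for a patient still event-free "at the last date of assessment of the WHO performance status, NPFS will be censored at that date". In section 8.2.3.3, only safety assessments made "before start of any further anti-cancer therapy will be included in the analysis".

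**Treatment before progression.** Under section 5.4, patients who stop therapy without progression "should usually not receive other cancer treatment before their disease progresses, unless this is clearly not in the interest of the patient". Section 8.3.2 reports the monitoring committee's advice to release the adjuvant comparison and to attend to arms 1-2, "who may benefit from initiating adjuvant TMZ and for whom a therapeutic decision to initiate such treatment may ensue".

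**The concern.** A progression-free interval means something only while progression is being looked for. If scheduled imaging may end at the start of another treatment while the PFS clock runs to the last visit or to death, a later radiological progression can be missed. The patient then has an event only at death, or is censored late as progression-free.

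The route in section 8.3.2 opens only for arms 1 and 2, which together are the no-adjuvant side of Question II. Apparent PFS would lengthen on that side alone, and the hazard ratio would move toward 1 in any Question II analysis made after the release. PFS is a secondary endpoint tested at 5% (section 8.2.3.2). Its only planned sensitivity analysis (section 8.2.4.1) is a per-protocol one, which does not address this. Without a written rule, the handling of these patients would be chosen after the data are seen.

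**Working it through.** **1. The texts side by side, for a patient who starts another treatment before documented progression**

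- Imaging: 7.1.1 permits a stop; 6.4.1 and 6.6 continue; 6.5 does not apply.
- PFS event: the first recorded progression or death (7.1, 8.2.1.2), at any later time.
- PFS censoring: last examination (7.1) or last visit (8.2.1.2). Neither must include a scan. Appendix M adds that visits may become telephone visits and that imaging may be skipped if it is impossible.

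If 7.1.1 is followed, the plan credits time without imaging as progression-free.

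**2. The plan's own figure**

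The plan gives no event count, median or power for PFS. Its OS figure reproduces. With HR 0.775, two-sided 5% and 83% power, the Schoenfeld formula gives

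d = 4(1.960 + 0.954)² / (ln 0.775)² = 33.97 / 0.0650 ≈ 523.

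Adding the 11 events stated for the interim look gives 534, as in section 8.1.1. This count does not depend on disease assessment and does not change.

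**3. Mechanism**

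If no progression is recorded after the switch, the PFS time of that patient runs to death. With an exponential time from progression to death of median 12 months (assumed), the mean excess is 12 / ln 2 = 17.3 months per switching patient, before the data cut-off truncates it.

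**4. Simulation A (all inputs assumed)**

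Inputs: median PFS 14 months; median from progression to death 14 months; switch at 2-5 months; cut-off uniform over 30-90 months; no progression recorded after the switch.

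| Share of arms 1-2 switching | True HR 0.62 estimated as | True HR 1.00 estimated as |
|---|---|---|
| 2% | 0.63 | 1.01 |
| 5% | 0.65 | 1.04 |
| 10% | 0.67 | 1.09 |

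Repeating the simulation moved these by no more than 0.01. If half of the later progressions are still recorded (assumed), the 0.62 column becomes 0.625, 0.637 and 0.647.

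**5. Simulation B (different assumptions)**

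Inputs: control median PFS 18 months; switch at 2-8 months; same cut-off; 300,000 patients per group; true PFS HR 0.775, borrowed from the OS design. Only the no-adjuvant group switches.

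| Median progression to death | 5% | 10% | 20% |
|---|---|---|---|
| 6 months | 0.786 | 0.799 | 0.819 |
| 12 months | 0.797 | 0.820 | 0.868 |
| 18 months | 0.805 | 0.838 | 0.907 |

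The column shares are nominal. About 4%, 8% and 16-17% actually switch, because a patient must still be progression-free at the switch. A true HR of 1.00 is estimated as 1.01-1.04, 1.03-1.08 and 1.07-1.17.

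If both groups switch equally, which is the Question I situation, 0.775 becomes 0.776-0.791. With no switching the simulation returns 0.776 and 1.004, so differences of a few thousandths are noise. Censoring at the switch returns 0.772-0.779, but only because switching is unrelated to prognosis in this simulation.

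**The case against.** **A reader might infer that these patients are not assessed at all.** The documents do not establish that. Sections 6.4.1 and 6.6 still schedule six-monthly imaging, and Appendix M says that remaining patients are followed for progression as well as survival. Clinical or neurological progression is also a PFS event (7.1, 7.1.2.2), and 7.1.1 does not disable it. Section 7.1.1 is the outlier. What stands is a contradiction that permits gaps in imaging.

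**The last visit is usually the disease assessment.** For a patient without progression the six-monthly visit includes imaging, and section 7.2 censors NPFS at the last examination just as 7.1 does for PFS. The contrast between the two endpoints is therefore confined to chapter 8. This reduces the gap in routine follow-up, but not where imaging has stopped or was skipped.

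**A reader might infer that the released adjuvant PFS result is biased.** The arms 1-2 route opens only after that release, so the result is largely unaffected by it. In Question I the switchers from arm 1 and arm 2 fall on opposite sides and largely balance. The documents also do not say whether adjuvant temozolomide taken on the committee's advice counts as another treatment under 7.1.1.

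**Censoring at new treatment is not a neutral cure.** Section 5.4 allows early treatment where withholding it would be against the patient's interest, which is plausibly linked to prognosis, so the censoring may be informative. Counting PFS regardless of new treatment fits the intention-to-treat rule in 8.2.3.1. This stands, and it is why neither rule should be used alone.

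**Conclusion.** The point holds as an internal conflict with a foreseeable but modest consequence. Section 7.1.1 disagrees with 6.4.1 and 6.6 on imaging after new treatment, and the PFS definitions do not take up the stop that 7.1.1 allows. Only patients treated before documented progression are affected, and the documents do not give their number.

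For Question II analyses made after the release, the direction is toward 1 if switching is confined to arms 1-2. The size is illustrative: 0.62 to 0.63-0.67 at 2-10% switching. These are upper-end values for a given switch rate, because they assume that no progression is recorded afterwards. Larger shifts need larger assumed switch rates or longer assumed survival after progression. The documents support no stronger claim: not that the released adjuvant result is compromised, nor that Question I is materially distorted, nor that censoring at new treatment is the one correct rule. OS is unaffected. This is a worthwhile improvement to a secondary endpoint and does not threaten the trial's conclusions.

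**What to change.** 1. Reconcile 7.1.1 with 6.4.1 and 6.6, so that the protocol states once whether scheduled disease assessment continues after another treatment starts. State also whether adjuvant temozolomide begun after the release counts as another treatment.
2. In 8.2.1.2, censor event-free patients at the last disease assessment instead of the last visit, as 8.2.1.3 does for NPFS. This alone does not reach a patient who dies after an unimaged interval, because the death remains an event; hence item 3.
3. Report PFS in two ways: censoring at the last assessment on or before the start of another anti-cancer treatment, and ignoring that treatment. Name in advance which is primary, consistent with the reconciled schedule. The version that ignores new treatment is only as good as the imaging obtained after the switch.
4. Report by arm how many patients started another treatment before progression.

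The cost is protocol and SAP wording, and slightly fewer PFS events or months of follow-up. The version that censors at new treatment may be informatively censored, which is why both are reported. No sample size figure changes.

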7.1.2 Definition of progression

Special attention should be given so as to avoid labeling progressive enhancement or edema which develops immediately after the end of radiotherapy as tumor progression. Pseudo-progression within the first three months from completion of radiotherapy is recognized to occur. (Ref. 19) Such pseudo-progression may continue for months, and may be accompanied by clinical signs and symptoms. Therefore, only in exceptional cases should the adjuvant treatment be discontinued or cancelled within 3 months of radiotherapy. In addition, surgery may cause increased contrast uptake, which should be differentiated from tumor progression. The clinical follow-up must dictate how the initial progression of the lesion should be labeled. If the course of events shows that true progression indeed occurred, the date of the first increase is to be considered as the date of progression. The study coordinator may be contacted for further discussions on a case by case basis.

7.1.2.1 Radiological progression

For follow-up it is required that the patients are followed with the same type of imaging throughout the whole study. The lesion –whether contrast enhancing or not- must be measured in the two largest perpendicular diameters, the area is defined as the product of these two diameters.

- Increase of contrast enhancing area on MRI or CT scans of more than 25% as measured by two perpendicular diameters compared to the smallest measurements ever recorded for the same lesion by the same technique.
- The appearance of new lesions with or without contrast enhancement
- In case of predominantly non-enhancing tumors: an increase of 25% in bi-dimensional perpendicular product of signal hyperintensity area on MRI T2 weighted images or FLAIR images, or area with hypodensity on CT scan

If there is radiological evidence of progression only before the first cycle of adjuvant treatment, patients may stop radiotherapy but should be continuing the adjuvant treatment. Such cases will be reviewed.

7.1.2.2 Clinical /neurological progression

Clinical/neurological progression is defined as the presence of the following conditions:

- decrease in WHO performance status
 - for patients with baseline WHO performance status 0: deterioration to WHO performance status 2 or worse for which no other explanation is present
 - for patients with baseline WHO performance status 1 or 2: deterioration to WHO performance status 3 or worse for which no other explanation is present
- deterioration of neurological functions
- appearance of signs/symptoms of increased intracranial pressure (headache, nausea and vomiting without other explanations)
- and/or start of corticosteroid or increase of corticosteroid dosage by 50% for control of neurological signs and symptoms

7.1.2.3 Considerations in the diagnosis of clinical/neurological progression

At all times in case of clinical/neurological progression, radiological confirmation of the progression is recommended.

In case no clear progression is visible as compared to recent neuro-imaging procedures older images must be used for comparison to detect progression.

If no clear progression is visible on neuro-imaging other explanations for the deterioration must be sought (e.g., anticonvulsant medication, metabolic disturbances)

7.2 Neurological deterioration free survival

This study will assess neurological deterioration as a secondary endpoint to investigate if the prolongation of progression free survival translates into a better preservation of neurological function. Neurological deterioration is defined as a decrease in WHO performance status as follows:

- decrease in WHO performance status
 - for patients with baseline WHO performance status 0: deterioration to WHO performance status 2 or worse for which no other explanation is present, and which is maintained for at least three months
 - for patients with baseline WHO performance status 1 or 2: deterioration to WHO performance status 3 or worse for which no other explanation is present and which is maintained for at least three months

The date of neurological deterioration will be the first date the persistent decrease in performance status was diagnosed. Neurological deterioration free progression is the time interval between the date of randomization and the date of neurological deterioration or death whichever occurs first. If neither event has been observed, the patient is censored at the date of the last follow up examination.

7.3 Evaluation of cognitive function

Short cognitive screening with the Mini-Mental State Examination (MMSE) will take place at randomization, 4 weeks after radiotherapy and then at every scheduled follow-up visit as indicated in chapter 6. This 30-point test includes questions on orientation to time and place, registration, attention, calculations, recall, language, and visual construction. (See Appendix L)

Additional more comprehensive neurocognitive testing will be performed at dedicated centers only, as a side study to this protocol. (See Appendix I)

7.4 Overall survival

All patients will be followed until death. The duration of survival is the time interval between randomization and the date of death due to any cause. Patients not reported dead or lost to follow up will be censored at the date of the last follow up examination.

7.5 Evaluation of toxicity

7.5.1 Adverse events and side effects

All adverse events will be recorded on the case report forms; the investigator will decide if those events are drug related (unrelated, likely related, not assessable) and his decision will be recorded on the forms for all adverse events.

Adverse events not drug related (i.e. reported as unrelated) will not be considered as side effects or toxicity.

7.5.2 General evaluation of side-effects

This study will use the International Common Terminology Criteria for Adverse Events (CTCAE), version 3.0, for toxicity and adverse event reporting. A copy of the CTCAE can be accessed from the CTEP home page (https://ctep.cancer.gov/protocoldevelopment/electronic_applications/docs/ctcae3.pdf). A link to this page is provided on the EORTC web site <http://www.eortc.org/>; if the location is moved to another site, this link will be updated. Investigators who do not have any access to Internet can contact the EORTC Headquarters to receive a copy by mail.

Hematological toxicity will be assessed on the basis of blood counts as indicated in chapter 6. The nadir count will be assessed for each cycle of therapy, and graded according to the International CTCAE v3.

Non-hematological acute side effects will be assessed and reported separately for each cycle of therapy, and graded according to the International CTCAE v3.

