6.3.1.1 Weekly visits

- Physical examination including vital signs
- Complete blood count (**temozolomide patients only**)
- Toxicity according to CTCAE v.3

6.3.1.2 Evaluation at week 4 and 6

- Physical examination including vital signs and neurological evaluation
- WHO-ECOG performance status
- Toxicity according to CTCAE v.3
- Complete blood count, all serum chemistries including LDH (**temozolomide patients only**)
- Corticosteroids intake

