8.2.3.3.1 Hematological parameters

For the whole treatment period, the worst value of each hematological parameter will be calculated for each patient. The worst value of each parameter will then be coded and the frequency of each category will be tabulated. A table with grade 3 or 4 rates will be provided.

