8.2.6 Data recording and display

Frequency tables will be tabulated (by treatment group or otherwise) for all categorical variables by the levels of the variables as they appear on the CRF (with %). Categories with a text field specification will be tabulated as categories and then supplemented by a listing with the following information for the patients fulfilling the condition for the specification (patient id, institution, treatment group, value of the item and text field contents).

Dates relating to events prior to entry will be presented as the delay in days (or weeks, months, or years) between the past event and the date of entry (date of randomization – date of past event + 1) and presented using the median and range. For example, on the randomization checklist, the date of last administration of prior treatment (or the date of first diagnosis of the cancer) will be presented as the time elapsed (in days, weeks, months or years, as appropriate) since the day of the last administration and the date of entry on study (date of randomization – last administration/diagnosis +1). Other delays (e.g. re-treatment delays) are presented as continuous variables using the median and range.

Continuous variables for which a coding system exists (such as for laboratory data) will be recoded into categories (for adverse events, the grading scale specified in the protocol will be used). Whenever no specific scale exists, lab data will be categorized based on the normal range: for example, below the lower normal limit (when appropriate), within the normal range, above the upper normal limit (UNL) and the degree to which it is above the UNL (for example > 2.5 x UNL, > 5 x UNL, > 10 x UNL). For laboratory data, the nadir is generally displayed. The nadir in a given cycle is the lowest laboratory value in that cycle; the overall nadir for a patient is the lowest laboratory value among all cycles.

Other continuous variables (for example age, dose ...) will be presented using the median and range (minimum, maximum).

If appropriate, continuous data may also be presented in categories.

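### Blood counts are scheduled very unequally across arms and adjuvant cycles, so worst-value grade 3–4 rates partly reflect how often patients were sampled, and a fixed day-28 cut can put the 4-week count in the wrong period

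*Combined protocol and SAP*

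**What the plan says.** Section 7.5.2 sets the source of the data, "Hematological toxicity will be assessed on the basis of blood counts as indicated in chapter 6", and then the measure: "The nadir count will be assessed for each cycle of therapy, and graded according to the International CTCAE v3". Section 8.2.6 defines the term: "The nadir in a given cycle is the lowest laboratory value in that cycle". The analysis in Section 8.2.3.3.1 is broader: "For the whole treatment period, the worst value of each hematological parameter will be calculated for each patient", followed by a table of grade 3 or 4 rates. Section 8.2.3.3 asks for safety results overall and by period.

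The sampling in chapter 6 is as follows.

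- During radiotherapy (Sections 6.3.1.1, 6.3.1.2 and 6.6), haematology is "mandatory only for temozolomide treated patients".
- Four weeks after radiotherapy (Section 6.3.1.3), there is one count in every arm.
- In the adjuvant phase (Section 6.4.2.1), there is one count before each cycle, in arms 3 and 4 only.
- On day 21 of a cycle (Section 6.4.2.2): "This is only needed in cycle 1 and in cycle 2 if the daily dosage is increased to 200 mg/m²", or where the previous cycle showed significant haematological toxicity.
- The six-monthly visits (Section 6.4.1) list no blood count.

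On timing, Section 8.2.3.3 has the radiotherapy period "end the day of the last administration of radiation therapy treatment plus 28 days". The adjuvant or follow-up period starts on day 29.

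**The concern.** The lowest of several counts depends on how many counts there are and when they are taken. If one arm contributes a single count and another about twenty, the worst-value table mixes any drug effect with the number of chances to record a low value. Within the adjuvant phase, a cycle nadir that rests on one end-of-cycle sample is simply that sample. A trough that has recovered by then goes unseen.

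The period boundary adds a separate problem. The 4-week visit falls on the edge of the radiotherapy period, and chapter 6 gives no window for it.

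Safety of concurrent and adjuvant temozolomide is a stated objective (Section 2.2) and toxicity is a secondary endpoint (Section 2.3.2). Readers will compare these tables across arms even though no test is attached.

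**Working it through.** The plan states no figure for haematological toxicity, so there is nothing to reproduce. The check counts scheduled samples and then illustrates what unequal counts can do.

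**1. Scheduled post-baseline counts for a patient completing treatment, without triggered tests**

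- Radiotherapy lasts 6.5 weeks (Section 5.2.1), which gives 6–7 weekly counts in arms 2 and 4 and none in arms 1 and 3. The week 4 and week 6 evaluations are taken to coincide with weekly visits.
- The 4-week post-radiotherapy visit gives 1 count in all arms.
- There are at most 12 adjuvant cycles (Section 5.2.2.4). The count before cycle 1 may be the same sample as the 4-week count, so pre-cycle counts add 11–12.
- Day 21 adds 1 count (cycle 1), or 2 if the dose is increased in cycle 2.

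| Arm | Sum | Counts |
|---|---|---|
| 1 | 1 | 1 |
| 2 | (6 to 7) + 1 | 7–8 |
| 3 | 1 + (11 to 12) + (1 to 2) | 13–15 |
| 4 | (6 to 7) + 1 + (11 to 12) + (1 to 2) | 19–22 |

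**2. Routine post-dose counts per adjuvant cycle**

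Cycle 1 has 2 (day 21 and before cycle 2), cycle 2 has 1–2, each of cycles 3–11 has 1 (before the next cycle), and cycle 12 has 0. Any further day-21 count follows significant haematological toxicity in the prior cycle. The weekly tests in Section 5.5.1 follow an interruption for toxicity. Both depend on toxicity already having been detected.

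**3. Effect of count frequency alone**

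Assume the same risk p of a grade 3–4 value at every count in every arm, that is, no treatment effect. Under independence the chance of at least one such value in k counts is 1 − (1 − p)^k.

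| p (assumed) | Arm 1 | Arm 2 | Arm 3 | Arm 4 |
|---|---|---|---|---|
| 0.5% | 0.5% | 3.4–3.9% | 6.3–7.2% | 9.1–10.4% |
| 1% | 1.0% | 6.8–7.7% | 12.2–14.0% | 17.4–19.8% |
| 2% | 2.0% | 13.2–14.9% | 23.1–26.1% | 31.9–35.9% |

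Counts within a patient are correlated, so independence exaggerates the spread. A beta-binomial model with mean p and intra-patient correlation ρ uses s = 1/ρ − 1, a = ps and b = (1 − p)s. The chance is then 1 − B(a, b + k)/B(a, b), where B is the beta function. At p = 1% and ρ = 0.5 the four arms show 1.0%, 2.6–2.7%, 3.1–3.3% and 3.5–3.6%. The gap shrinks but remains.

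**4. Missed late troughs**

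Assume a true grade 3–4 rate of 2% in each of cycles 3–12, independent between cycles. The chance of any event is 1 − 0.98^10 = 18.3%. Let r be the share of troughs that have recovered above the cut-off by the count before the next cycle. With no triggered counts and none after cycle 12, the table would show 1 − (1 − 0.02(1 − r))^9:

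- r = 20%: 13.5%
- r = 50%: 8.6%
- r = 80%: 3.5%

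**5. Period boundary**

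A 4-week visit held exactly on time is day 28 and stays in the radiotherapy period. On day 29 or later it falls into follow-up in arms 1 and 2. If the treatment period is read as excluding follow-up, arm 1 then has no scheduled on-treatment count. In arms 3 and 4 the same visit falls into the adjuvant period, possibly before any adjuvant dose. In arm 4 a low count after concurrent temozolomide would then appear as an adjuvant-period finding.

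**The case against.** The other side has a good deal to say.

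- A reader might infer that the per-cycle nadir cannot be produced at all. The documents do not support that. Section 8.2.6 defines it as the lowest laboratory value in the cycle, so it can be computed wherever a count exists. In most late cycles it is a single pre-next-cycle value, which is a limit on interpretation.
- A reader might infer that the tables are bound to understate temozolomide toxicity. That does not follow. The only haematology table in Section 8.2.3.3.1 uses the whole-period worst value, and the early day-21 counts feed it. Patients are affected only if their worst count comes later and is not sampled. More counts enlarge an apparent temozolomide excess, while missed troughs shrink it.
- Some late toxicity is recovered by triggered day-21 counts (Section 6.4.2.2) and weekly tests during interruptions (Section 5.5.1). This holds, but it makes sampling depend on outcome.
- The documents do not say whether a pre-cycle count belongs to the cycle ending or the one starting. Under the second convention cycle 12 does have a value, though a pre-dose one.
- Section 8.2.3.3.4 rules out formal safety comparisons, and by-period tables help. Arms 2 and 4 share a schedule during radiotherapy, and arms 3 and 4 share one during adjuvant treatment. Both factorial contrasts nevertheless remain unequally sampled: concurrent versus none during radiotherapy, and adjuvant versus none afterwards.
- The boundary problem affects only visits after day 28, and the documents do not say how often that happens.

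**Conclusion.** The point holds as a reporting weakness that should be corrected. Scheduled counts differ about 20-fold between arms 1 and 4. Routine late-cycle sampling is one end-of-cycle count in cycles 3–11 and no post-dose count in the last cycle. A worst value over more counts can only be equal or worse, and one over fewer counts can only miss low values. Grade 3–4 rates therefore partly reflect sampling frequency.

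The schedule counts come from the documents. The percentages do not: they rest on assumed per-count risks, correlation and recovery shares, and show only what is possible. Neither the size nor the net between-arm direction of the distortion can be determined. The overall survival analysis is not affected.

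**What to change.** 1. In Section 8.2.3.3, assign the 4-week post-radiotherapy count to the radiotherapy period by visit name, provided it precedes the first adjuvant dose.
2. Add a four-arm grade table at that visit, the only post-baseline count scheduled in every arm. With k = 1 throughout, unequal scheduled frequency no longer affects the comparison.
3. Show whole-period and by-period worst values with the number of patients having at least one count and the median number of counts per arm. State that concurrent versus no concurrent during radiotherapy, and adjuvant versus no adjuvant afterwards, are not sampled alike.
4. Keep every recorded count in the worst value. In any per-cycle table, separate scheduled day-21 counts, toxicity-triggered counts and pre-next-cycle counts, with the number sampled for each. Align the nadir wording of Sections 7.5.2 and 8.2.6, and say to which cycle a pre-cycle count belongs.

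The cost is some SAP wording and a few extra tables. Appendix M records that all patients have completed study treatment, so on-treatment sampling can no longer change. The fix needs no new samples and leaves the monitoring schedule as it is.
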